Mild Intermittent Hypoxia and CPAP: A Multi-Pronged Approach to Treat Sleep
Apnea in Intact and Spinal Cord Injured Humans

Record # 1 R56HL142757-01

Date: November 5th 2018

Experimental Protocol

Specific Aim 1. To determine if IH coupled with CPAP mitigates autonomic, cardiovascular, neurocognitive and metabolic measures both directly and indirectly by improving CPAP compliance as a consequence of LTF of upper airway muscle activity initiated by exposure to IH.

a. Rationale. Many studies have reported that IH directly mitigates co-morbidities typically associated with OSA. In addition, exposure to IH may increase CPAP compliance by initiating LTF of upper airway muscle activity that could enhance upper airway patency leading to a reduction in therapeutic CPAP. Reduced pressures could result in improved compliance and outcome measure.

b. Recruitment. The participants with OSA may be recruited from Sleep Disorders Centers affiliated with Wayne State University and John D. Dingell Veterans Administration Medical Center. The total number of patients studied in these laboratories per year is approximately 4500 and about 40 % of the participants will meet the inclusion criteria. We will also target hypertension clinics at John D. Dingell VA Medical Center and the Detroit Medical Center as additional sites to recruit participants with coincident hypertension and OSA; since up to 30 % of individuals diagnosed with hypertension also have been diagnosed with OSA. Advertisements will also be placed in the local newspaper (i.e. Metro Times) and on various websites (i.e. Craigslist, Facebook and Wayne State University Pipeline). During recently completed studies approximately 100 individuals were screened in order to recruit 20 participants that met the inclusion criteria. In the present proposal we believe this rate of recruitment will improve because our inclusion criteria is less stringent than in the past (i.e. previously we recruited individuals with OSA that fell within a narrow age range and did not suffer from other co-morbid conditions). Based on past experience, once participants meet the inclusion criteria and have successfully completed the screening sleep study and practice trial few drop out beyond this point. Nonetheless we have taken into account that 2 participants from each group (see Participants below) may drop out beyond the point of the screening and practice trials, so an additional 4 participants may be enrolled if required.

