Visits 5, 12 & 19: On visits 5, 12 & 19 additional autonomic, cardiovascular, neurocognitive and metabolic measures will be obtained. Upon entering the laboratory participants will complete a series of questionnaires and tasks to assess vigilance and neurocognitive function. The Pathfinder Number Test and Psychomotor Vigilance Task will assess attention and psychomotor function. The Buschke Selective Reminding Test will assess learning and memory. The Epworth Sleepiness Scale will assess day time sleepiness. The Mini Mental State Examination will be used

to assess five areas of cognition function (i.e. orientation, registration attention, calculation, recall and language). Thereafter, 15 ml of blood will be sampled prior to exposure to the IH or sham protocol to identify potential metabolic (i.e. lipid profile, hemoglobin A1C), inflammatory (i.e. asymmetric dimethylarginine and high sensitivity C-reactive protein) and angiogenic/vasculogenic (hypoxia inducible factor 1 α and vascular endothelial growth factor) biomarkers that might reflect the efficacy of exposure to IH. Thereafter, on visits 5 & 19 beat to beat measures of blood pressure will be obtained throughout the IH or sham protocol. Beat to beat measures of blood pressure will also be obtained on visit 12. On visits 12 & 19 daytime exposure to the IH or sham protocol will be followed by a sleep study completed in the laboratory on the evening following the day time visit. Measures obtained during these sleep studies will be similar to the measures described for Visit 3. Visit 20: The protocol outlined for Visit 4 will be repeated on Visit 20.

Data and Statistical Analysis.

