Research staff that will not administer the gases will be assigned to complete a blind analysis of all measures. The staff assigned to analyze data (e.g. ventilation and blood pressure) collected during the direct application of hypoxia might be able to determine the applied stimulus based on the respiratory or cardiovascular response. However, the criteria used to analyze the data is rigorous and bias is unlikely. The Shapiro-Wilk test will be used to test if the data is normally distributed. Assuming that the data will be normally distributed, a two-way analysis of variance with repeated measures in conjunction with Student-Newman Keuls post-hoc test will be used to determine if differences in 24 hour blood pressure measures are evident before and after exposure to IH or the sham protocol. The two factors in the design will “Group (Hypoxia vs. sham)” and “time point (Visit 4 vs. Visit 20).” A similar analysis will be used to determine if primary (i.e. blood pressure, autonomic nervous system activity, therapeutic CPAP, critical closing pressure, limb motor function tests) and secondary (vigilance and neurocognitive measures and blood biomarkers) outcome measures differ before, midway and after completion of the IH or sham protocol. The two factors in the design will be “Group (Hypoxia vs. sham)” and “time point (Visit 5 vs. Visit 12 vs. Visit 19)”. Primary outcome variables collected during IH or the sham protocol (i.e. blood pressure, autonomic nervous system activity, minute ventilation, tidal volume, breathing frequency, PETCO₂, PETO₂) will be analyzed using a three-way analysis of variance with repeated measures in conjunction with Student-Newman Keuls post hoc. The three factors in the design will be “Group (Hypoxia vs. sham)”, “Visit Number (Visit 5 vs. Visit 12 vs. Visit 19)” and “Time Point (Baseline vs. Initial hypoxic episode vs. Final hypoxic episode vs recovery of IH or sham protocol).” A Pearson product-moment correlation and regression analysis will be used to examine the relationship between CPAP adherence (e.g. percentage of days CPAP used over 4 or 6 hours) during the last half of the protocol with changes in the primary and secondary outcome measures for hypoxia and sham groups. If CPAP adherence impacts on the primary and/or secondary outcome measures we expect the slope of the relationship will be greater in Hypoxia group compared to sham group (i.e. for a given level of adherence modification to the primary or secondary outcome variable will be greater in the CPAP and IH group compared to the CPAP and sham group).

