IH protocol from 3 to at least 10 weeks, since a wash-out period would be required between IH and sham. Given concerns that the protocol could be too long, we believe a parallel design is appropriate. (ii) Exposure to mild IH during sleep in untreated participants might result in increased breathing instability. This potential problem will not be an issue in the present study. Participants will be exposed to IH while awake during daytime hours. Likewise, participants will be treated with CPAP during sleep and we anticipate that therapeutic CPAP will be reduced while sleep apnea is effectively treated as the protocol progresses. Nonetheless, the CPAP instrument that we utilize monitors the AHI each night. If there is an unexpected increase in apnea severity the participant will be asked to withdraw from the study. (iii) We anticipate that sympathetic nervous system activity and blood pressure will be reduced in response to mild forms of IH coupled with CPAP. However, if progressive increases in blood pressure are evident over 3 visits that equate to sustained increases in systolic and diastolic blood pressure of greater than 10 mmHg the participants will be withdrawn from the study. Because the participants are coming to the laboratory each day changes in health status will be monitored day to day. (iv) The instrumentation and methods employed during sleep on Visits 3, 5, 12 and 19 could lead to disruption of sleep and the inability to collect the planned measures. Given the population we are employing this is typically not an issue when the participants are treated with CPAP. Nonetheless, all measurements will be obtained during deep N2 or N3 of non-rapid eye movement sleep and a sleep efficiency of at least 75 % will be required. If these criteria are not obtained a repeat sleep study will be completed on the following day. (v) Participants will be blinded to the composition of the gas mixture. However, they may recognize increases in heart rate and breathing during IH exposure. During the consenting process we will describe potential responses that might be experienced during each visit to all participants, without linking the responses to IH exposure. Based on past experience naïve participants often do not directly associate increases in breathing and heart rate with IH. Nevertheless, at least one of our outcome measures will allow us to differentiate if knowledge of the gas mixture, or other factors, influenced our results. More specifically, measures of the critical closing pressure during sleep should not be influenced by knowledge of the gas mixture. If CPAP compliance improves without a coincident improvement in the critical closing pressure we would question if knowledge of the gas mixture, or other factors, are influencing our results.

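### The apnea and blood pressure stopping rules end study participation, not only the gas sessions, so participants who worsen lose their final primary outcomes

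*Combined protocol and SAP*

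**What the plan says.** Potential Problems & Solutions (ii) relies on the nightly AHI recorded by the CPAP device and states: "If there is an unexpected increase in apnea severity the participant will be asked to withdraw from the study". It gives no size, reference value or duration for the increase. Item (iii) covers progressive blood pressure rises over 3 visits that amount to a sustained increase of more than 10 mmHg; in that case "the participants will be withdrawn from the study". Neither item offers the option of stopping IH or sham and staying on for the outcome visits.

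Data and Statistical Analysis lists the primary outcomes as "blood pressure, autonomic nervous system activity, therapeutic CPAP, critical closing pressure, limb motor function tests". It compares 24-hour blood pressure at Visit 4 and Visit 20, and it tests whether primary and secondary "outcome measures differ before, midway and after completion of the IH or sham protocol", with Visits 5, 12 and 19 as the time points. Both comparisons use a two-way repeated-measures ANOVA. No analysis set is defined, and nothing is said about participants with incomplete data.

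Therapeutic CPAP and critical closing pressure are measured in the sleep studies of Visits 3, 12 and 19. For the last two the plan says: "Measures obtained during these sleep studies will be similar to the measures described for Visit 3". Section c (Participants) sets 4 participants per group. Section b (Recruitment) allows for two losses per group after the practice trial and concludes: "so an additional 4 participants may be enrolled if required".

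**The concern.** The two rules do not remove people at random with respect to the outcomes. Item (iii) acts directly on a primary outcome: a participant leaves because blood pressure moved the wrong way. Item (ii) acts on a measure close to two other primary outcomes. The plan's expectation is that "we anticipate that therapeutic CPAP will be reduced while sleep apnea is effectively treated as the protocol progresses", so a rise in AHI on CPAP is evidence against that expectation.

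If IH worsens apnea or blood pressure in some participants, those are the people without final values. The Hypoxia group at Visits 19 and 20 would then consist of those who were not harmed. The same tilt could arise without true harm if staff read the undefined trigger in item (ii) more readily in one arm than in the other. The planned blind analysis cannot correct this, because there are no later data to analyse.

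**Working it through.** **The plan's own figure.** 2 dropouts per group x 2 groups = 4 extra participants, as stated. The maximum enrolled is 4 + 4 + 4 = 12. The documents give no alpha, power, effect size or SD, so there is no power calculation to reproduce.

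**What a removed participant lacks.** This follows from Table 1 and the analysis section.
- Removed before Visit 12: no midway or final therapeutic CPAP or critical closing pressure, and no Visit 20 24-hour blood pressure.
- Removed between Visits 12 and 19: the midway values exist; the Visit 19 and Visit 20 values do not.

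The plan does not say that earlier data are discarded. A conventional repeated-measures ANOVA, however, normally drops anyone without a complete set of time points. One removal is 1/4 = 25% of a group. Two are 2/4 = 50% of the planned group, or 2/6 = 33% of the 6 who could be enrolled per group.

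**Illustration with an exact rank test** (two-sided; the plan itself uses ANOVA). Suppose three Hypoxia participants do better than all Sham participants, and a fourth worsens and is removed. Any replacement also does better than all Sham participants. Rank 1 is best.

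| Analysis | Hypoxia ranks | Exact p |
|---|---|---|
| Completers with replacement, 4 v 4 | 1, 2, 3, 4 | 2/70 = 0.029 |
| Completers without replacement, 3 v 4 | 1, 2, 3 | 2/35 = 0.057 |
| Removed participant kept as worst, 4 v 4 | 1, 2, 3, 8 | 24/70 = 0.34 |
| Kept as worst, replacement added, 5 v 4 | 1, 2, 3, 4, 9 | 24/126 = 0.19 |

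**Selection when IH has no effect.** Assume that the participant with the worst AHI change is removed in the Hypoxia arm only. Assume also a correlation rho of 0.3 to 0.8 between AHI change and outcome change, and a replacement who is a fresh draw. None of these inputs is in the documents. The expected maximum of 4 standard normal values is 1.029.
- Not replaced: shift = 1.029 x rho / 3. For rho = 0.3, 0.5, 0.8 this is 0.10, 0.17, 0.27 SD.
- Replaced: shift = 1.029 x rho / 4, which gives 0.08, 0.13, 0.21 SD.
- Standard error of the group difference, 4 v 4: sqrt(1/4 + 1/4) = 0.71 SD. For 3 v 4: sqrt(1/3 + 1/4) = 0.76 SD.

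The shift favours IH and is at most about 0.27/0.76 = 0.36 of a standard error. With removal applied alike in both arms and no IH effect, the expected shifts cancel.

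**The case against.** The strongest reply is that these are precautionary safety stops in a very small study of hypoxia, and that an investigator should be free to act at once. That stands, and the fix leaves it untouched. Several further points also have weight.

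- The rules as written cover both groups, so bias needs either real harm from IH or uneven application. This is correct, and the point is conditional for that reason.
- Likelihood is not established. IH is given by day to awake participants, CPAP is used at night, and the recruitment section reports few losses after screening. The documents give no basis for a removal rate.
- Item (ii) is worded as a request, and the replacement allowance speaks of dropout without naming rule-based removals. Counting such removals as dropouts is a fair reading, not a stated rule. The loss of final values does not depend on it.
- Under no effect the distortion is small even with removal in the Hypoxia arm only. Simulated t-tests give a two-sided error of about 5.1 to 6.4% in place of a nominal 5%.
- The lack of a missing-data rule is a general gap. It matters more here because these two rules create missing values that are related to outcome.

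A reader might infer from the rank table that a single removal decides the trial's result. The documents do not support that. The case is constructed, and it falls below 0.05 only if a replacement is enrolled and also does well. Without one, the contrast is 0.057 against 0.34. The plan states no alpha and does not use a rank test, and a rise in device AHI does not show that a person would rank worst on every primary outcome.

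**Conclusion.** The point holds as a low-cost improvement to consider, not as a demonstrated bias. The text is clear that both rules end study participation and that the analysis has no provision for those removed. The direction of any tilt is towards IH. It arises only if IH harms some participants or the rules are applied differently by arm. Its size under no effect is modest, 0.08 to 0.27 SD, on the assumed correlations and removal in one arm only. Its size under real harm cannot be stated from the documents.

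A reader might also infer that the completer comparison would turn net harm into apparent benefit. If three participants improve by b and one worsens by h, the whole-group mean change is (h - 3b)/4, with positive values meaning harm, while the three completers show -b. The sign reverses only when h exceeds 3b. Nothing in the documents supports a harm of that size or a harmed share of one in four.

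**What to change.** Amend items (ii) and (iii) and the analysis section in a few sentences.

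1. On a trigger, stop the IH or sham sessions but keep CPAP and keep the participant in follow-up. If the participant and physician agree, carry out the Visit 19 sleep study and the Visit 20 24-hour recording without gas exposure.
2. Keep every randomised participant in the group comparison. Add any replacement to the group; do not substitute it for the person who stopped. Report stops by arm and reason.
3. Add a sensitivity analysis that ranks a stop for worsening as the worst outcome.
4. Keep the investigator's freedom to stop a participant at once. Have staff who do not give the gases apply the rules alike in both arms.

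A numeric AHI threshold tied to Visit 3 is not recommended. That night is used for titration and critical closing pressure, and it gives no clear steady AHI on CPAP to serve as a reference.

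The cost is one sleep study and one 24-hour recording per stopped participant, both already in the schedule. The target sample size does not change. The downsides are that some participants will decline, measures taken early follow fewer sessions than planned, and the worst-rank analysis has less power.

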c. Participants. To complete the R56 proposal, Hypoxia group will be comprised of 4 participants with OSA that will be treated with IH and CPAP. Sham group will be comprised of 4 participants with OSA that will be exposed to a sham protocol and CPAP. Participants will be randomized to Hypoxia or Sham group. Participants will be male or female of any race, 18-60 years of age with a BMI of less than 40 kg/m² and pure or predominantly (i.e. comprised of both a central and obstructive component) OSA (AHI \leq 80 events per hour and an average oxygen desaturation level of 85 % or greater). Participants will not have received CPAP treatment previously. Participants' will be diagnosed with Stage 1 to Stage 2 hypertension as categorized by the 2018 American Heart Association guidelines. Systolic and diastolic pressure will range from 130 - 159 mmHg and 80 - 99 mmHg, respectively. Participants with a systolic pressure greater than 159 mmHg or a diastolic pressure greater than 99 mmHg will be excluded from the study. Based on the characteristics of this group the short exposure to mild IH that we will induce does not pose a risk beyond what exists for participants without OSA based on previous studies we have completed. Moreover, the nocturnal oxygen desaturation routinely experienced by the recruited participants will be mild, which will reduce the possibility of central nervous system hypoxic depression. Thus, we believe that initiation of various forms of plasticity following exposure to IH may manifest themselves more clearly in these individuals. The participants will be free of any other known cardiovascular disease. The participants will not be on any medications used to treat

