
(ventilation, PETCO₂, PETO₂, oxygen saturation) and cardiovascular (heart rate and EKG) parameters will be monitored continuously throughout each visit. Likewise, with the exception of visits 5, 12 and 19 (see immediately below) automated and auscultatory blood pressure measurements will be obtained prior to the onset of the protocol, during hypoxic episodes 1, 6 and 12, during recovery from these episodes, as well as, at the midpoint and completion of the end recovery period of the IH or sham protocol. On each day of the protocol participants will continue to be treated with CPAP each night while they sleep in their home environment with the exception of visits 12 and 19 (see Table 1 below). They will be instructed to use CPAP each night for as long as possible.

| | Consent & Screening | Diagnostic Sleep Study | CPAP Titration & PCRT | IH or Sham | Blood Draw | Beat to Beat Blood Pressure | Automated Blood Pressure | Neurocognitive Testing |
|----------|---------------------|------------------------|-----------------------|------------|------------|-----------------------------|--------------------------|------------------------|
| Visit 1 | ✓ | | | | | | ✓ | |
| Visit 2 | | ✓ | | | | | ✓ | |
| Visit 3 | | | ✓ | | | | ✓ | |
| Visit 4 | | | | | | | ✓ | |
| Visit 5 | | | | ✓ | ✓ | ✓ | ✓ | ✓ |
| Visit 6 | | | | ✓ | | | ✓ | |
| Visit 7 | | | | ✓ | | | ✓ | |
| Visit 8 | | | | ✓ | | | ✓ | |
| Visit 9 | | | | ✓ | | | ✓ | |
| Visit 10 | | | | ✓ | | | ✓ | |
| Visit 11 | | | | ✓ | | | ✓ | |
| Visit 12 | | | ✓ | ✓ | ✓ | ✓ | ✓ | ✓ |
| Visit 13 | | | | ✓ | | | ✓ | |
| Visit 14 | | | | ✓ | | | ✓ | |
| Visit 15 | | | | ✓ | | | ✓ | |
| Visit 16 | | | | ✓ | | | ✓ | |
| Visit 17 | | | | ✓ | | | ✓ | |
| Visit 18 | | | | ✓ | | | ✓ | |
| Visit 19 | | | ✓ | ✓ | ✓ | ✓ | ✓ | ✓ |
| Visit 20 | | | | | | | ✓ | |

Table 1. Planned measures for each visit to the laboratory (Aim 1). CPAP – continuous positive airway pressure; IH – intermittent hypoxia; PCRT – critical closing pressure

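### Read literally, the only numeric on-study blood-pressure withdrawal rule needs both pressures to rise; changing one word would let either trigger it, for a modest safety gain

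*Combined protocol and SAP*

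**What the plan says.** Potential Problems & Solutions (iii) anticipates that pressure will fall, and provides for the opposite case. The rule starts "if progressive increases in blood pressure are evident over 3 visits" and applies when these amount to "sustained increases in systolic and diastolic blood pressure of greater than 10 mmHg the participants will be withdrawn from the study". The next sentence adds: "Because the participants are coming to the laboratory each day changes in health status will be monitored day to day".

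The only other numeric blood-pressure limit that removes anyone is the entry criterion under c. Participants: "Participants with a systolic pressure greater than 159 mmHg or a diastolic pressure greater than 99 mmHg will be excluded from the study". That section admits people at 130-159 systolic and 80-99 diastolic, and states "The participants will not be on any medications used to treat" cardiovascular disorders.

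Under d. Protocol and Measurements, pressure is taken before, during and after exposure at most of the 15 exposure visits. Visits 5, 12 and 19 are set apart: "with the exception of visits 5, 12 and 19 (see immediately below) automated and auscultatory blood pressure measurements will be obtained prior to the onset". Table 1 ticks automated pressure at those three visits without giving a time. No action value is attached to any of these readings.

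Recruitment (section b) allows for 2 dropouts per group, "so an additional 4 participants may be enrolled if required".

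**The concern.** A withdrawal rule with a number in it exists so that stopping does not depend on judgement alone. This one joins the two pressures with *and*. Applied as written, it is silent on a sustained rise of any size in one pressure while the other moves by 10 mmHg or less.

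The people concerned have stage 1-2 hypertension and take no drugs for cardiovascular disorders. Those in the Hypoxia group receive twelve two-minute episodes of 8% oxygen at each of 15 visits. For them the rule bears on whether exposure continues. Sham participants breathe room air, so for them it bears only on staying in the study.

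**Working it through.** **1. The rule as logic.** Literal reading: withdraw if the systolic rise is > 10 and the diastolic rise is > 10, with the pattern seen over 3 visits. Alternative: withdraw if either rise is > 10, with the same pattern.

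- 150/90 to 185/99: 185 − 150 = +35; 99 − 90 = +9. Literal rule not met; either-pressure rule met.
- +12/+12: both rules met. +8/+8: neither met.
- Entry at the upper limit, 159/99: 159 + 10 = 169 and 99 + 10 = 109. The either-pressure rule acts above 169 or above 109. The literal rule sets no systolic limit while diastolic stays at or below 109.

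This step needs no assumption beyond the example values.

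**2. The two limits side by side.** The entry exclusion uses *or*, so either pressure alone disqualifies. It stands among the recruitment characteristics, and nothing extends it past enrolment. The other withdrawal provision, in item (ii), concerns apnea severity and has no blood-pressure element.

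**3. How much the word matters: simulation.** The documents give no visit-to-visit variability, so every input here is an assumption:

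- SD (systolic/diastolic) 5/3, 8/5 or 10/6 mmHg, and correlation 0.5 or 0.7;
- bivariate normal readings, independent between visits, at the 14 visits from 6 to 19;
- reference equal to the mean of two comparable pre-exposure readings;
- trigger when three consecutive visits are each more than 10 mmHg above the reference. *Strict* also requires each of the three readings to exceed the one before;
- 100,000 participants per setting. Ranges run across the SDs and correlations.

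| True change | *and* | *or* | strict *and* | strict *or* |
|---|---|---|---|---|
| None | 0-2.2% | 1.6-18% | 0-0.2% | 0.4-6% |
| Step to +20/+5 | 4-22% | 92-99.6% | 0.3-3% | 64-83% |
| Step to +20/+15 | 79-98% | 96-99.9% | 17-45% | 78-95% |

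A step rise is not the gradual pattern that the rule describes. With a ramp to +20/+5 reached by Visit 19, and without the strict condition, *and* triggers in about 1-11% and *or* in about 71-88%. The contrast is the same in kind.

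**4. Cost in false withdrawals.** For 8 independent participants with no true rise, the chance of at least one is 1 − (1 − p)^8:

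- *or*: 1 − (1 − 0.0157)^8 = 12%, up to 1 − (1 − 0.1846)^8 = 80%.
- strict *or*: 1 − (1 − 0.0039)^8 = 3%, up to 1 − (1 − 0.0613)^8 = 40%.
- *and*: 0%, up to 1 − (1 − 0.022)^8 = 16%.

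One withdrawal is 1/4 = 25% of a group.

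**The case against.** The strongest reply is that no defect is proved. *Systolic and diastolic* can simply name the two pressures being watched, and c. Participants uses the pair that way when it gives the entry ranges. The *or* in the entry exclusion shows that the authors can write an either-pressure rule. It does not show that they meant *and* strictly here. This stands. A reader might infer that the investigators intend a both-pressures rule, but the text does not settle that.

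Second, participants are seen daily and pressure is measured at every exposure visit. The 185/99 example supposes that staff see 185 repeatedly and do nothing. A reader might infer that an isolated rise would go unattended, and the documents do not support that either. What remains is that the monitoring sentence sets no limit, so the action would rest on judgement alone.

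Third, the +20/+5 scenario was chosen to be discordant, and its inputs come from outside the documents. This also stands. With a concordant rise of +20/+15 and no strict condition, the gap is much smaller. The simulation illustrates the mechanism and is not a forecast for this trial.

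Fourth, accepting more false withdrawals in exchange for an either-pressure trigger is a trade between safety and completion, and in a 4-versus-4 trial it is a real one. That is why the cost is set out above.

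**Conclusion.** The point holds as a cheap improvement with a modest safety gain. On its literal wording, the sole numeric on-study blood-pressure rule does not require withdrawal for a sustained rise in one pressure alone, however large. That follows from the text without assumptions.

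How often the wording would matter cannot be taken from the documents. It depends on how discordant a rise is, on visit-to-visit variability, and on how strictly *progressive* is read. The false-withdrawal rates rest on the assumed SDs and correlations and on a reference comparable with the later readings. A reference that runs low would make the *or* rates worse.

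**What to change.** In Potential Problems & Solutions (iii), replace *and* with *or* between the two pressures. Keep the progressive increase over 3 visits and the requirement that the rise be sustained. The one-word change does not depend on anything further.

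Because an *or* rule is more sensitive to noise, apply it to the resting reading taken before exposure. Compare that with a daytime reference obtained before the first exposure, for example the mean of Visit 1 (if held by day) and Visit 5 before exposure. Leave out readings taken around the sleep studies at Visits 2 and 3. This reference has two visits, and repeat readings within a visit would not average out visit-to-visit variation, so the two-reading rates above are the ones to plan on. It would help to say whether a step rise that then stays level counts as progressive, since that choice moves the false-withdrawal rate between roughly 1.6-18% and 0.4-6%.

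The cost is one word, plus placing the cuff reading already ticked in Table 1 before exposure at Visits 5, 12 and 19. No visit or staff is added. The price in completion is the extra false withdrawals, against which Recruitment already allows 2 dropouts per group and 4 further participants.
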